#### **5.4. Study Treatment**

All eligible subjects will be treated with ibrutinib PO and MEDI4736 IV in 28-day cycles. On infusion days where pharmacokinetic, pharmacodynamic or biomarker samples are taken post dose, MEDI4736 IV should be given first, followed by that day's ibrutinib dose. Missed doses of ibrutinib and MEDI4736 will not be made up. Dose escalation of any agent (ibrutinib or MEDI4736) at any time will not be allowed. MEDI4736 will be given for a maximum of 12 months. Re-treatment with MEDI4736 will not be allowed following completion of 12 months of treatment, regardless of any dose delays or missed doses. Treatment with ibrutinib will continue for up to 3 years or until disease progression or unacceptable toxicity.

##### **5.4.1. Phase 1b**

Two dose levels of ibrutinib (560 or 420 mg/day) and 2 dose levels of MEDI4736 (10 or 3 mg/kg IV every 2 week) may be tested. The starting dose will be 560 mg ibrutinib PO daily and MEDI4736 10 mg/kg IV every 2 weeks.

##### **5.4.2. Phase 2**

Subjects will be administered ibrutinib and MEDI4736 at the RP2D determined during the Phase 1b portion of the study.

#### **5.5. Study Medication**

##### **5.5.1. Ibrutinib**

###### **5.5.1.1. Formulation/Packaging/Storage**

Ibrutinib capsules are provided as a hard gelatin capsule containing 140 mg of ibrutinib. All formulation excipients are compendial and are commonly used in oral formulations. Refer to the [ibrutinib IB](#) for a list of excipients.

The ibrutinib capsules will be packaged in opaque high-density polyethylene plastic bottles with labels bearing the appropriate label text as required by governing regulatory agencies. Study drug will be dispensed in child-resistant packaging.

Refer to the Pharmacy Manual/site investigational product manual for additional guidance on study drug storage, preparation and handling.

Study drug labels will contain information to meet the applicable regulatory requirements.

### 5.5.1.2. Dose and Administration

Ibrutinib 560 mg (4 x 140-mg capsules) or 420 mg (3 x 140-mg capsules) is administered orally once daily. The capsules are to be taken around the same time each day with 8 ounces (approximately 240 mL) of water. The capsules should be swallowed intact and subjects should not attempt to open capsules or dissolve them in water. The use of strong CYP3A inhibitors/inducers and grapefruit and Seville oranges should be avoided for the duration of the study ([Appendix 5](#)).

If a dose is not taken at the scheduled time, it can be taken as soon as possible on the same day with a return to the normal schedule the following day. The subject should not take extra capsules to make up the missed dose.

The first dose of ibrutinib will be administered in the clinic on Day 1 (after the end of the MEDI4736 infusion), after which subsequent dosing is typically on an outpatient basis. Subjects will be provided a daily drug diary to record ibrutinib doses. Ibrutinib will be dispensed to subjects in bottles at appropriate visits. When a new bottle is dispensed, unused ibrutinib dispensed during previous visits must be returned to the site and drug accountability records ([Section 12.8](#)) should be updated. Returned capsules must not be redispensed to anyone.

### 5.5.1.3. Overdose

Any dose of study drug administered in excess of that specified in this protocol is considered to be an overdose. Signs and symptoms of an overdose that meet any SAE criterion must be reported as a SAE in the appropriate time frame and documented as clinical sequelae to an overdose.

There is no specific experience in the management of ibrutinib overdose in patients. No MTD was reached in the Phase 1 study in which subjects received up to 12.5 mg/kg/day (1400 mg/day). Healthy subjects were exposed up to single dose of 1680 mg. One healthy subject experienced reversible Grade 4 hepatic enzyme increases (AST and ALT) after a dose of 1680 mg. Subjects who ingested more than the recommended dosage should be closely monitored and given appropriate supportive treatment.

Refer to [Section 11](#) for further information regarding AE reporting.

### 5.5.1.4. Dose Modification for Adverse Reactions

The dose of ibrutinib should be modified according to the dose modification guidance in [Table 2](#) if any of the following toxicities occur:

- Grade 4 neutropenia (ANC <500/ $\mu$ L) for more than 7 days. See [Sections 6.1](#) and [6.3](#) for instructions regarding the use of growth factor support.

- Grade 3 thrombocytopenia (platelet count  $<50,000/\text{mm}^3$  ( $50 \times 10^9/\text{L}$ ) in the presence of grade 2 or greater bleeding events.
- Grade 4 thrombocytopenia (platelet count  $<25,000/\text{mm}^3$  ( $25 \times 10^9/\text{L}$ )).
- Grade 3 or 4 nausea, vomiting, or diarrhea if persistent, despite optimal anti-emetic and/or anti-diarrheal therapy.
- Any other Grade 4 or unmanageable Grade 3 toxicity.

For Grade 3 or 4 atrial fibrillation or persistent atrial fibrillation of any grade, consider the risks and benefits of ibrutinib treatment. *If clinically indicated, the use of anti-coagulants or anti-platelet agents may be considered for the thromboprophylaxis of atrial fibrillation (Section 6.2.3).*

In the event that the investigator feels deviation from the recommendations above is required, please consult the medical monitor to discuss for approval.

If the dose of ibrutinib is reduced, at the Investigator's discretion, the dose of ibrutinib may be re-escalated after 2 cycles of a dose reduction in the absence of a recurrence of the toxicity that led to the reduction. Dose changes must be recorded in the Dose Administration eCRF.

**Table 2. Ibrutinib Dose Modifications**

Occurrence	Action to be Taken
First	Withhold study drug until recovery to Grade $\leq 1$ or baseline; may restart at original dose level
Second	Withhold study drug until recovery to Grade $\leq 1$ or baseline; may restart at 1 dose level lower (ie, 420 mg/day for original 560 mg/day dose; 280 mg/day for original 420 mg/day dose)
Third	Withhold study drug until recovery to Grade $\leq 1$ or baseline; may restart at 1 dose level lower (ie, 280 mg/day for original 560 mg/day dose) or discontinue for original 420 mg/day dose
Fourth	Discontinue study drug

If TLS is diagnosed, follow the institutional guidelines for management.

Study treatment should be discontinued in the event of a toxicity lasting more than 28 days, unless reviewed and approved by the Medical Monitor.

For required dose modification for hepatic impairment refer to [Section 5.5.1.5](#) and for concomitant treatment with CYP3A inhibitors refer to [Section 6.2.1](#).

### **5.5.1.5. Dose Modification for Hepatic Impaired Subjects**

Ibrutinib is metabolized in the liver and therefore subjects with clinically significant hepatic impairment at the time of screening (Child-Pugh class B or C) are excluded from study

participation. For subjects who develop mild liver impairment while on study (Child-Pugh class A), the recommended dose reduction for ibrutinib to a level of 280 mg daily (two capsules). For subjects who develop moderate liver impairment while on study (Child-Pugh class B), the recommended dose reduction is to a level of 140 mg daily (one capsule). Subjects who develop severe hepatic impairment (Child-Pugh class C) must hold study drug until resolved to moderate impairment (Child-Pugh class B) or better. Monitor subjects for signs of toxicity and follow dose modification guidance as needed (Refer to [Appendix 9](#)).

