  - Serum aspartate transaminase (AST) or alanine transaminase (ALT)  $\leq 2.5 \times$  upper limit of normal (ULN) for subjects without liver metastases and  $\leq 3.5 \times$  ULN for subjects with liver metastases
  - Bilirubin  $\leq 1.5 \times$  ULN (unless bilirubin rise is due to Gilbert's syndrome or of non-hepatic origin)
  - Creatinine  $\leq 2.0 \times$  ULN and Creatinine Clearance  $\geq 40 \text{ mL/min}$  (Cockcroft-Gault or 24-hour creatinine clearance collection)
7. Prothrombin time (PT)/International normalized ratio (INR)  $< 1.5 \times$  upper limit of normal (ULN) and partial thromboplastin time (PTT)/ activated partial thromboplastin time (aPTT)  $< 1.5 \times$  ULN
8. Men and women  $\geq 18$  years of age
9. Eastern Cooperative Oncology Group (ECOG) performance status of 0 or 1
10. Female subjects must either be of non-reproductive potential (ie, post-menopausal by history:  $\geq 60$  years old and no menses for  $\geq 1$  year; OR history of hysterectomy; OR history of bilateral

tubal ligation; OR history of bilateral oophorectomy). Female subjects of reproductive potential must have a negative serum pregnancy test upon study entry.

11. Male and female subjects of reproductive potential who agree to use highly effective methods of birth control (eg, condoms, implants, injectables, combined oral contraceptives, some intrauterine devices [IUDs], complete abstinence, or sterilized partner) during the period of therapy and for 90 days after the last dose of study drug (see [Appendix 8](#)).
12. Men must agree to not donate sperm and a woman must agree to not donate eggs (ova, oocytes) for the purposes of assisted reproduction during or for 3 months after the last dose of either drug.

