#### **4.2. Exclusion Criteria**

To be enrolled in the study, potential subjects must meet **NONE** of the following exclusion criteria:

1. Subjects with tumors of mixed small cell and NSCLC histology
2. Central nervous system (CNS) involvement of disease except as follows: Subjects with previously treated CNS metastases that are adequately treated with whole brain radiotherapy (+/- surgery), that are neurologically stable, and do not require corticosteroids (of any dose) for symptomatic management for at least 14 days prior to first dose of MEDI4736 plus ibrutinib. In addition, there must be no clear evidence of radiographically active disease for at least 90 days prior to enrollment.
3. Anti-tumor therapy (chemotherapy, antibody therapy, immunotherapy, biologic-based therapy, molecularly- targeted therapy, radiation therapy or investigational agent) within 21 days of study Day 1 (six weeks for nitrosureas, mitomycin C, or antibody or molecular targeted agents with  $t_{1/2} > 10$  days; 10 weeks for radio- or toxin-immunoconjugates); concurrent use of hormone deprivation therapy including but not limited to anastrozole, letrozole, or tamoxifen citrate for breast cancer and hormonal replacement therapy for non-cancer related conditions is permitted. Enrollment of subjects that have received molecularly-targeted small molecule inhibitors less than 21 days prior to study Day 1 will be permitted if more than 14 days and at least 5 drug half-lives have passed prior to receiving the first dose of ibrutinib.
4. Prior treatment with ibrutinib or other BTK inhibitor, anti-CD137 or anti-cytotoxic T-lymphocyte associated antigen 4 (CTLA-4) antibody. The following are exceptions to this criterion:
  - Subjects previously treated with anti-PD1, anti-PD-L1, or anti-PD-L2 antibody
5. Known allergy or hypersensitivity to ibrutinib or MEDI4736 or any excipients
6. Current or prior use of immunosuppressive medication within 14 days before the first dose of MEDI4736. The following are exceptions to this criterion:
  - Intranasal, inhaled, topical corticosteroids, or local corticosteroid injections (eg, intra-articular injection)

- Systemic corticosteroids at doses not to exceed 10 mg/day of prednisone or its equivalent
- Corticosteroids as pre-medication for hypersensitivity reactions (eg, CT scan pre-medication).

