*Subjects who are positive for hepatitis B core antibody, hepatitis B surface antigen, or hepatitis C antibody must have a negative polymerase chain reaction (PCR) result before enrollment. Those who are PCR positive will be excluded.*

16. History of primary immunodeficiency

17. Known history of previous clinical diagnosis of tuberculosis
18. Any uncontrolled active systemic infection or pneumonitis or interstitial lung disease
19. Major surgery within 4 weeks of the first dose of study drug
20. Any life-threatening illness, medical condition, or organ system dysfunction that, in the investigator's opinion, could compromise the subject's safety or put the study outcomes at undue risk, eg psychiatric illness/social situations that would limit compliance with study requirement or compromise the ability of the subject to give written informed consent.
21. Currently active, clinically significant cardiovascular disease, such as uncontrolled arrhythmia or Class 3 or 4 congestive heart failure as defined by the New York Heart Association Functional Classification; or a history of myocardial infarction, uncontrolled hypertension or cardiac arrhythmia, unstable angina, or acute coronary syndrome within 6 months prior to enrollment ([Appendix 6](#))
22. Unable to swallow capsules or active malabsorption syndrome not controlled by medication, disease or conditions significantly affecting gastrointestinal function, or complete resection of the stomach, or complete resection of small bowel, or partial or complete bowel obstruction
23. Concomitant use of warfarin or other Vitamin K antagonists
24. Treatment with a strong CYP3A inhibitor ([Appendix 5](#))
25. Pregnant or lactating female; men planning to father a child or women planning a pregnancy while taking study drug or within 3 months after the last dose of study drug
26. Concurrent enrollment in another clinical study, unless in a follow-up period or it is an observational study.
27. Unwilling or unable to participate in all required study evaluations and procedures
28. Unable to understand the purpose and risks of the study and to provide a signed and dated informed consent form (ICF) and authorization to use protected health information (in accordance with national and local subject privacy regulations)

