## **5. TREATMENT OF SUBJECTS**

### **5.1. Treatment Allocation**

This is an open-label study (both Phase 1b and Phase 2). After the subject has completed all baseline (screening) procedures and met all requirements of the inclusion/exclusion criteria, study site personnel can enroll the subject. All enrolled subjects will receive open-label ibrutinib capsules and MEDI4736.

Two dose levels of ibrutinib (560 or 420 mg/day) and MEDI4736 (10 or 3 mg/kg IV Q2 weeks) may be tested ([Table 1](#)). The starting dose will be 560 mg of ibrutinib PO daily and 10 mg/kg of MEDI4736 IV Q2 weeks. The dose may be modified based on the number of DLTs observed.

In each cohort, a sentinel subject will have a 3-day observation period prior to dosing of subsequent subjects to monitor for unexpected acute toxicities.

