###### **7.1.1.2. Confirm Eligibility**

All necessary procedures and evaluations must be performed to document that the subject meets all of the inclusion criteria and none of the exclusion criteria ([Section 4](#)).

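### The exclusion of Child-Pugh class B or C hepatic impairment in Protocol 5.5.1.5 is missing from the enrolment criteria and has no screening score to support it

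*Protocol*

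**What the plan says.** **The exclusion.** Protocol Section 5.5.1.5 says that "subjects with clinically significant hepatic impairment at the time of screening (Child-Pugh class B or C) are excluded from study" participation. The same section recommends 280 mg daily if class A impairment develops on study and 140 mg daily for class B. For class C, drug is held until the impairment improves to class B or better.

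**The enrolment check.** Section 4.2 opens with "To be enrolled in the study, potential subjects must meet" none of the criteria that follow, of which there are 28. Section 5.1 provides that, once a subject has completed screening and "met all requirements of the inclusion/exclusion criteria, study site personnel can enroll the subject". Section 7.1.1.2 asks sites to "document that the subject meets all of the inclusion criteria and none of the exclusion criteria" and points to Section 4.

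**The listed hepatic limits.** Inclusion 6 caps AST or ALT at 2.5 x ULN (3.5 x ULN with liver metastases). It caps bilirubin at 1.5 x ULN, waived for Gilbert's syndrome or a non-hepatic cause. Inclusion 7 requires PT/INR and PTT/aPTT below 1.5 x ULN. The synopsis repeats these limits. None of the 12 inclusion or 28 exclusion criteria names Child-Pugh class, albumin, ascites or encephalopathy.

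**Screening procedures.** Section 8.1.1 and the screening columns of Appendices 1 and 2 list no Child-Pugh score. Appendix 9 gives the scoring table and is cited only from Section 5.5.1.5.

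**The concern.** The protocol sets a categorical safety exclusion in a place that the enrolment procedure does not consult. Sections 4 and 5.5.1.5 do not contradict each other; Section 4 is silent.

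The silence looks like an omission. The hepatitis exclusion stated in Section 7.1.2.7 also appears as exclusion 15. In Section 4.2, exclusions 21 and 24 point to Appendices 6 and 5. No criterion points to Appendix 9.

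What is at stake is dosing safety. In Phase 1b the starting dose is 560 mg daily (Section 5.1). In Phase 2, "Subjects will be administered ibrutinib and MEDI4736 at the RP2D" chosen in Phase 1b, which means 420 or 560 mg of ibrutinib. Section 1.4.2.1 reports that a single dose gave an 8.2-fold higher ibrutinib AUC in class B subjects than in subjects with normal liver function. A subject whom 5.5.1.5 is meant to keep out could meet every listed criterion and start at full dose.

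**Working it through.** The question is whether the listed limits already keep class B subjects out, so that the missing line would not matter. There is no plan figure to reproduce; the check uses the plan's own scoring table.

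**Inputs.** From Appendix 9:
- Bilirubin below 2 mg/dL scores 1.
- INR below 1.7 scores 1.
- Albumin above 3.5, 2.8–3.5 and below 2.8 g/dL score 1, 2 and 3.
- Ascites none, mild and moderate-to-severe score 1, 2 and 3.
- No encephalopathy scores 1.
- Totals of 5–6 are class A, 7–9 class B and 10–15 class C.

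From Section 4.1: bilirubin at most 1.5 x ULN and INR below 1.5 x ULN.

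**Step 1: what the two caps do.** The documents give no ULN, so a range is assumed.
- Bilirubin stays at 1 point while 1.5 x ULN is below 2, that is, ULN below 2/1.5 = 1.33 mg/dL. For ULN 1.0–1.3 the cap is 1.50–1.95 mg/dL, so 1 point. At ULN 1.4 it is 2.10, so 2 points become possible.
- INR stays at 1 point while 1.5 x ULN is at most 1.7, that is, ULN at most 1.7/1.5 = 1.13. For ULN 1.0–1.1 the cap is 1.50–1.65, so 1 point. At ULN 1.2 it is 1.80, so 2 points become possible.

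The caps thus hold these two items at 1 point, or sometimes allow 2. A higher ULN can only allow a higher score.

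**Step 2: what the caps leave open.** Set bilirubin, INR and encephalopathy at 1 point each. The total is then 3 + albumin points + ascites points:

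| Albumin (g/dL) | No ascites | Mild | Moderate-to-severe |
|---|---|---|---|
| above 3.5 | 5 (A) | 6 (A) | 7 (B) |
| 2.8–3.5 | 6 (A) | 7 (B) | 8 (B) |
| below 2.8 | 7 (B) | 8 (B) | 9 (B) |

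Six of the nine combinations are class B. The three smallest routes are:
- low albumin alone: 3 + 3 + 1 = 7
- moderate-to-severe ascites alone: 3 + 1 + 3 = 7
- intermediate albumin with mild ascites: 3 + 2 + 2 = 7

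All three satisfy the bilirubin and PT/INR limits, whatever the ULN. The Gilbert's or non-hepatic bilirubin waiver is not needed for any of them. These are score combinations, not patient frequencies.

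**Step 3: the dose contrast.** Against the 140 mg recommended for class B arising on study, the assigned dose is 560/140 = 4 times or 420/140 = 3 times as large.

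**Step 4: whether the inputs exist at screening.** Albumin and total bilirubin are in the serum chemistry (Section 7.1.2.2). PT and INR are in the coagulation panel (Section 8.1.1). The physical examination covers the abdomen and nervous system (Section 7.1.1.6), and CT of the abdomen and pelvis is required before treatment (Section 7.1.3.2.1). All five items can be scored; the protocol does not ask for it.

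**The case against.** The strongest reply concerns what the score means in these patients. Section 5.5.1.5 ties the class to clinically significant hepatic impairment, and Appendix 9 is titled for subjects with liver impairment. The lowest possible total, 5, is already class A, which 5.5.1.5 calls mild impairment, so the score makes sense only once liver disease is present. In advanced cancer, low albumin or ascites can come from the tumour. Section 7.2.1.2 treats ascites as a form of non-measurable disease, and Section 7.1.3.6 speaks of fluid collected during the study, not of hepatic ascites at entry. This stands. A reader might infer that every score of 7 or more is a subject whom the sponsor meant to exclude; the documents do not support that.

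A reader might also infer that subjects let through would have about eight times the intended exposure. The 8.2-fold figure is a single-dose result in subjects with hepatic impairment. It may overstate exposure where bilirubin and INR are near normal and the points come from tumour-related findings.

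Safeguards exist:
- Section 5.5.1.5 binds investigators wherever it sits, and monitoring under Section 12.9 covers the whole protocol.
- ECOG status must be 0 or 1.
- Exclusion 20 covers "Any life-threatening illness, medical condition, or organ system dysfunction that" the investigator judges could compromise safety.
- Section 8.2.1.1 requires the Day 1 chemistry to be reviewed for eligibility before treatment.
- Phase 1b has a sentinel subject and weekly chemistry in Cycle 1, and Section 5.5.1.4 provides for withholding drug for toxicity.

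These reduce the risk but do not close the gap. Exclusion 20 is discretionary and names no class, and the Day 1 review has no albumin limit to check against. Monitoring and toxicity rules act after enrolment or dosing, and none of the listed checks puts the 5.5.1.5 exclusion before the person confirming eligibility.

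**Conclusion.** The point holds in a limited form. A binding exclusion for clinically significant hepatic impairment (Child-Pugh class B or C) is absent from the criteria that sites enrol on and from the synopsis, and no score is scheduled to apply it. The bilirubin and PT/INR limits do not stand in for it, because albumin and ascites alone can reach class B. A site following Sections 5.1 and 7.1.1.2 to the letter could enrol a subject whom 5.5.1.5 excludes and start at three or four times the dose recommended for class B arising on study.

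The number of such subjects is unknown, and none is claimed. The three routes rest only on Appendix 9; the ULN range bears on how firmly the caps hold bilirubin and INR at 1 point. It would go too far to say that the protocol permits class B subjects, since 5.5.1.5 forbids them. This is a subject-safety omission worth correcting. It has no bearing on the endpoints, the two-stage design or any analysis.

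**What to change.** Add one exclusion to Section 4.2 and the synopsis, keeping the qualifier used in 5.5.1.5: *Clinically significant hepatic impairment at screening (Child-Pugh class B or C; Appendix 9)*. Leave 5.5.1.5 as it is.

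Add a derived Child-Pugh score to Section 8.1.1 and to the screening columns of Appendices 1 and 2, from the albumin, bilirubin, PT/INR, physical examination and CT already obtained. Have the investigator document whether low albumin or ascites is hepatic or tumour-related. Keeping the qualifier and recording the cause avoids turning the rule into a mechanical cut-off that removes subjects whose score does not reflect the liver.

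The cost is one line in two places, one derived field with a short attribution note, and possibly a few more screen failures, for which the documents give no figure. No new procedure is needed.
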